2.1 Background

Pulmonary arterial hypertension (PAH) is a debilitating, progressive, and fatal complication of systemic sclerosis (SSc). Epidemiologic data show that patients with SSc-associated PAH (SSc-PAH) have a poor prognosis. While hemodynamic parameters such as right atrial pressure and cardiac index are predictors of survival in WHO group I PAH, they are relatively crude and indirect markers of RV performance in PAH [162, 163]. Interestingly, we have recently demonstrated that in comparison to other diseases with associated PAH, SSc-PAH is characterized by less severe hemodynamic perturbation, but also a more robust neurohormonal activation and worse 1-year survival [164]. These findings suggest that the right ventricular response to PAH in systemic sclerosis may differ from that seen in other etiologies of PAH and potentially plays an important role in shaping the natural history of this form of PAH.

Recent studies have demonstrated the utility of MRI based protocols for evaluation of right ventricular performance in PAH [165, 166]. Protocols which evaluate RV structure and function supplement the routine hemodynamic measures obtained during cardiac catheterization and add additional dimensions to the evaluation of disease and response to therapies. On the one hand, the measures from MRI are more directly related to the pathophysiology of right ventricular injury than are the less direct (but widely employed) measures of right atrial pressure and cardiac index, or the even further removed index of 6-minute walk distance (6MWD). Thus, these MRI measures, while perhaps less directly clinically applicable than 6MWD, do offer the potential for a more precise delineation of the cardiac impact of a given therapy such as rituximab. These data will be complementary to

pulmonary vascular resistance (PVR), which is a more pure vascular measure. Additionally, the reproducibility of the MRI measures of RV function is very high, so relatively small changes can be detected and thus MRI offers the hope of detecting early cardiac remodeling changes even if a full clinical impact is not yet demonstrable.

2.2 Rationale

PAH is a cardiopulmonary disease manifested by increased PVR due to obliterative arteriopathy. The increase in PVR creates increased pressure work for the right ventricle. Clinical evidence suggests that the capacity of the right ventricle to respond to this increase in afterload by remodeling may be a critical determinant of disease progression and overall prognosis [167-169]. Although right heart catheterization (RHC) is the gold standard for diagnosis of PAH, the hemodynamic measures which are obtained during RHC do not appear to provide comprehensive evaluation of RV function nor do they offer accurate prognosis for all forms of PAH [170]. For example, patients with PAH resulting from congenital heart diseases are typically characterized by very poor hemodynamics, yet these patients have among the best survival of any PAH cohort. One potential explanation for this is the long-standing and early onset of adverse hemodynamics in such patients, which may allow for more effective right ventricular remodeling.

Specifically relevant to the ASC01 study is the role of RV performance in SSc-PAH. Using a large multicenter PAH registry, we have recently demonstrated that SSc-PAH ([name], [name] unpublished data) patients had the most favorable hemodynamics as demonstrated by lower mean pulmonary artery pressure, higher cardiac index and lower PVR when compared to idiopathic PAH and other autoimmune-associated PAH. Despite this apparently favorable hemodynamic profile, the 1 year survival for SSc-PAH was worse when compared with the other cohorts. This again supports the idea that it is not hemodynamic profile alone that determines prognosis, but rather the cardiac response to these hemodynamics in the form of RV remodeling.

Cardiac MRI allows for a comprehensive non-invasive evaluation of RV chamber size, myocardial mass and systolic function, providing information which is complementary to that obtained by cardiac catheterization. Evaluation of baseline RV status using cardiac MRI in SSc-PAH and the response to rituximab will help determine the role which RV remodeling plays in shaping the overall patient outcome in PAH, and may also demonstrate a mechanism by which rituximab affects disease outcome, if such effect is found.

The RESTORE sub-study will further help delineate the utility of cardiac MRI in studying treatment response in PAH. While there have been some data evaluating this, there is not yet adequate data to specify which markers of RV remodeling will be most useful in evaluating the evolution of patients with PAH. The RESTORE sub-study, by providing MRI data in a well-characterized set of patients, will help better define this question as well.

2.3 Significance

This sub-study is likely to enhance the capacity of the ASC01 study in evaluation of response of SSc-PAH to rituximab therapy by evaluating a set of outcomes which are complementary

to secondary study aims, but which are more focused on right ventricular performance. This will assist in evaluating the factors contributing to the clinical outcomes observed in the main study by providing data which help clarify the cardiac responses during therapy. These data will help clarify the contribution to outcome that arises from the vascular outcome of PVR.

3 Study Overview

3.1 Overall Study Design

The RESTORE sub-study will include all sites participating in the primary ASC01 study that have the capability to perform the required MRI studies. Enrollment within the RESTORE sub-study will consist of consecutive ASC01 study subjects at each site, provided that the subject provides consent for this separate sub-study. This should diminish any unintentional bias in patient selection at each site. Thus, both placebo and rituximab arms will be included in the RESTORE sub-study. Twenty subjects from each arm will be recruited into this sub-study. Each subject will be studied at baseline (i.e. prior to initiation of study drug) and at Week 24, or at time of discontinuation. Subjects in RESTORE will undergo comprehensive cardiac MRI evaluation. Given that the primary comparison is a pre/post match, and that the MRI interpretation is performed by individuals blinded to the treatment assignment, it is not likely to introduce bias if one or more sites cannot participate in the RESTORE sub-study. However, should this be the case, the overall study population will be compared to the sub-population captured at these sites with respect to baseline characteristics. Since the RESTORE sub-study will use the same entry criteria as the parent protocol, there should not be a problem with differential patient selection, with the exception of the additional exclusion criteria specified below that relate to the contra-indications to MRI. While it does not appear likely that these criteria will bias the sub-study population, the data analysis will again compare the baseline characteristics of study subjects for the parent protocol to that of the RESTORE sub-study.

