3 STUDY DESIGN

3.1 Description of Study Design

This is a prospective, double-blind, placebo-controlled, multi-center, randomized trial to evaluate the effect of rituximab on disease progression in subjects with SSc-PAH receiving concurrent stable-dose standard medical therapy with a prostanoid, endothelin receptor antagonist, phosphodiesterase 5 (PDE-5) inhibitor, and/or guanylate cyclase stimulators. The study will focus on assessment of clinical response and safety measures longitudinally. In addition, the effects of treatment with rituximab on the underlying immune mechanisms associated with B-cell dysregulation and pathogenic autoantibody response in this disease will be investigated.

Subjects with SSc-PAH with elevated mean pulmonary artery pressure as measured by right heart catheterization will be enrolled. The diagnosis of SSc-PAH should be confirmed by a rheumatologist experienced in the diagnosis and treatment of systemic sclerosis in conjunction with a pulmonologist or cardiologist specializing in management of PAH. Both specialists will be part of the study team at each site.

Rituximab/placebo will be administered as two IV infusions of 1000 mg each, given two weeks apart at Day 0 and Week 2. All subjects will receive 40mg of prednisone orally the night before and morning of each infusion, as well as 100 mg methylprednisolone or equivalent corticosteroid intravenously approximately thirty minutes prior to each infusion with diphenhydramine and acetaminophen orally approximately thirty to sixty minutes prior to each infusion of rituximab or placebo. Subjects will remain on their baseline standard medical regimen.

Sixty eligible subjects will be accrued. Each potential study subject will provide written informed consent prior to screening procedures. All inclusion and exclusion criteria (Section 4, *Selection of Subjects*) must be met at time of randomization prior to receipt of the first dose of rituximab/placebo (Day 0, Treatment Initiation).

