3.2 Study Population

3.2.1 Inclusion Criteria

Each participant included in this sub-study must be a participant in and meet the inclusion criteria for the ASC01 clinical protocol. In addition, written informed consent for the RESTORE sub-study must be provided.

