8.2 Sample Size

The sample size for this sub-study is determined in large part by the size of the parent protocol and budget considerations. With these factors in mind, a sample size of 20 subjects in each arm (40 total subjects) is feasible.

Data from van Wolferen indicate that in subjects with pulmonary hypertension, RVEDVI determined by cardiac MRI was 85 ± 25 ml/m². Assuming that the standard deviation does not change during the sub-study, and that there is a 10% (8.5 ml/m²) mean reduction in right ventricular volume index over the placebo group, one obtains the following relationship between the percent reduction and the expected power:

A mean reduction of 10% would power this sub-study at 27.8%. A recent study of resynchronization therapy for left ventricular failure demonstrated a reduction in left ventricular systolic volume index of approximately 15% of the baseline value; if this level is found, the power would increase to 47.6% [172].

Since the main purpose of the RESTORE sub-study is to get a better understanding of how rituximab affects RVEDVI for subsequent research studies, this level of power will suffice.

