8.3 Statistical Analysis of Study Objectives

The primary aim of this sub-study is a comparison of the change in RVEDVI between the rituximab and the placebo arm of the parent trial, in subjects who have cardiac MRI at baseline and at Week 24, or at time of discontinuation. This comparison will be made using an ANCOVA model with change in RVEDVI as the response and treatment, center, and baseline value as covariates. It is not anticipated that non-parametric tests will be required, but the data distribution will be evaluated and suitable data transformation will be performed as needed. However, based upon experience in other studies using similar outcomes, such is not likely to be required [165, 166]. A p-value of 0.05 will be taken as the threshold for significance. For the secondary outcomes of RV mass and stroke volume, a similar analysis will be performed.

9 Safety Monitoring and Reporting

Monitoring and reporting of any adverse events associated with MRI procedures for this sub-study will be the responsibility of the clinical sites and will be reported to the IND holder using the standard mechanisms implemented as described in Section 7, *Safety Monitoring and Reporting*, of the ASC01 clinical protocol which is incorporated by reference for this sub-study.

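### RESTORE's check for selective enrolment compares the whole trial with a sub-study nested inside it, so at 40 of 60 subjects it displays only one-third of any difference between participants and non-participants

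*Protocol*

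**What the plan says.** Appendix F, section 3.1 (Overall Study Design), argues that neither missing sites nor the extra MRI exclusions are likely to bias the sub-study, and plans a baseline comparison for each.

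- **Missing sites.** If one or more sites cannot participate, "the overall study population will be compared to the sub-population captured at these sites with respect to baseline characteristics". This is conditional, and it is unclear whether "these sites" means those taking part or those that cannot.
- **MRI exclusions.** The section's last sentence carries no condition: "the data analysis will again compare the baseline characteristics of study subjects for the parent protocol to that of the RESTORE sub-study".

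The groups are nested. Appendix F, section 3.2.1, states: "Each participant included in this sub-study must be a participant in and meet the inclusion criteria for the ASC01 clinical protocol". On size, Appendix F, section 8.2, says "a sample size of 20 subjects in each arm (40 total subjects) is feasible", and section 3.1 of the main protocol says "Sixty eligible subjects will be accrued".

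Appendix F names no test, standard error or criterion of similarity for either comparison. Its only significance threshold, "A p-value of 0.05 will be taken as the threshold for significance", is in section 8.3 and belongs to the RVEDVI analysis. The SAP text does not mention the check, and neither document plans to compare participants with non-participants.

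**The concern.** Selection into RESTORE is plausible. Section 3.1 requires an MRI-capable site and separate consent. Section 3.2.2 excludes subjects who cannot tolerate or cooperate with MRI, are morbidly obese, have metallic objects or a pacemaker, or are hypersensitive to gadolinium. These features could go with different baseline severity.

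The check is the plan's own evidence on this point. When the comparator contains the group being checked, two-thirds of it at the planned sizes, the two columns are pulled together whatever the data. At stake is how far RESTORE's right-ventricular results can be read alongside the 6MWD and PVR results of the full trial, a use that the sub-study synopsis and section 2.3 of Appendix F both have in view.

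**Working it through.** **Plan's own figure.** None is given for this check. The only calculation in Appendix F, section 8.2, is the RVEDVI power, based on "RVEDVI determined by cardiac MRI was 85 ± 25 ml/m²". With 20 per arm, SD 25 and a t test at one-sided 0.05, it reproduces at 27.8% for a 10% reduction (8.5 ml/m²) and 47.6% for 15% (12.75 ml/m²). That confirms 20 per arm as the planned size and has no other bearing here.

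**Inputs.** RESTORE 40 (Appendix F, section 8.2); ASC01 60 (Protocol section 3.1); all 40 are among the 60 (Appendix F, section 3.2.1), leaving 60 − 40 = 20 non-participants.

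**Step 1: what is displayed.** Let P and N be the participant and non-participant means. The whole-trial mean is (40P + 20N)/60, so

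P − (40P + 20N)/60 = (20/60)(P − N).

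This is exact and assumes no test. A gap of 0.5 SD is shown as 0.17 SD, and 0.8 SD as 0.27 SD. With n participants the factor is 1 − n/60: one-half for 30 and two-thirds for 20.

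**Step 2: standard errors, in SD units.**

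- Ordinary two-sample formula, 40 vs 60, overlap ignored: √(1/40 + 1/60) = 0.204.
- Actual standard error of the overlapping difference: (1/3) × √(1/40 + 1/20) = (1/3) × 0.274 = 0.091.

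**Step 3: detection if the overlap were ignored.** This is an assumption, because the plan names no test. At two-sided 0.05 the displayed difference must exceed 1.96 × 0.204 = 0.400. For a true gap of 0.8 SD, (0.400 − 0.267)/0.091 = 1.46, giving 7.2% by the normal formula. Simulated t tests (40,000 per effect size) give 3.5%; the figure is lower because the gap itself inflates the pooled SD.

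| True gap | Displayed | Detected, 40 vs 60, overlap ignored (simulated t to normal formula) | Detected, 40 vs 20 (t test) |
|---|---|---|---|
| 0.5 SD | 0.17 SD | 0.3% to 0.5% | 43% |
| 0.8 SD | 0.27 SD | 3.5% to 7.2% | 82% |
| 1.0 SD | 0.33 SD | 12.5% to 23% | 95% |
| 1.2 SD | 0.40 SD | 32% to 50% | 99% |
| 1.5 SD | 0.50 SD | 69% to 86% | about 100% |

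With no true gap, the overlap-ignoring test rejects about 0% of the time instead of 5%.

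**Step 4: sensitivity.** For a 0.8 SD gap (normal formula), the overlap-ignoring test detects 38% with 30 of 60 in RESTORE, against 87% for 30 vs 30. With 20 of 60 it detects 56%, against 83% for 20 vs 40.

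**Step 5: a test that allows for the overlap.** At 0.8 SD its ratio is 0.267/0.091 = 2.92, the same as 0.8/0.274 = 2.92 for 40 vs 20. Handled correctly, the overlap costs no power.

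**The case against.** The strongest reply is that no test is proposed. The plan says only that baseline characteristics will be compared, and SAP section 5.2 handles baseline data with descriptive statistics. A reader might infer from the detection rates that the protocol uses a wrong standard error, or that even a large difference would almost never be found. The documents support neither reading: the rates belong to an assumed analysis, a correct one loses nothing (Step 5), and very large gaps would often be found even when the overlap is ignored. This objection stands, and it limits the firm finding to Step 1.

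A second reply is that the smaller number answers a fair question, namely how far the RESTORE mean lies from the trial mean. The non-participant mean can also be recovered as (60 × overall − 40 × RESTORE)/20. Both statements are true for means on complete data. However, section 3.1 offers the comparison as reassurance about patient selection, and the direct measure of selection is the gap between those who joined and those who did not. A reader should not have to back-calculate it, and its confidence interval would not be shown.

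Third, 40 is a feasibility target, so one-third is the factor at plan. Fewer participants would mean less dilution.

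Finally, a reader might infer that RESTORE's treatment comparison is biased. It is not biased by this: assignment comes from the parent randomisation, images are read without access to assignment, and no conclusion in Appendix F is made to depend on the check.

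**Conclusion.** The point holds as a matter of presentation and representativeness. The unconditional comparison at the end of Appendix F, section 3.1, sets all ASC01 subjects against a subset of themselves. At the planned 40 of 60 it displays one-third of the difference between participants and non-participants. That factor is algebra and depends only on the numbers enrolled.

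The detection figures rest on further assumptions: an ordinary two-sample test that ignores the overlap, two-sided 0.05, and normal data with a common SD. They describe what could happen under an analysis the plan leaves open, and should not be read as what the plan prescribes. The conditional site-level comparison shares the part-against-whole form, but its groups are ambiguous and their sizes unstated, so the 40-of-60 arithmetic should not be attached to it.

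The consequence is small. It affects how confidently RESTORE can be called representative of ASC01.

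**What to change.** In Appendix F, section 3.1, replace the overlapping comparison with RESTORE participants versus ASC01 subjects not in RESTORE. If some sites cannot take part, compare subjects at participating sites with subjects at non-participating sites, which also removes the ambiguity over which sites are meant.

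Report standardised differences with 95% confidence intervals for age, NYHA class, 6MWD, PVR and BNP/NT-proBNP. State that similarity will not be inferred from p > 0.05: with 40 versus 20 the interval is about ±1.96 × 0.274 = ±0.54 SD, so a non-significant result would still leave room for a material difference.

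The cost is a change of wording and one table. All five variables are already collected at screening or baseline (Protocol sections 6.5.1 and 6.5.2) and are already listed for summary in SAP section 5.2.

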3.2 Study Population

3.2.1 Inclusion Criteria

Each participant included in this sub-study must be a participant in and meet the inclusion criteria for the ASC01 clinical protocol. In addition, written informed consent for the RESTORE sub-study must be provided.

3.2.2 Exclusion Criteria

Each participant included in this sub-study must not meet any of the exclusion criteria for the ASC01 clinical protocol. In addition, subjects who meet any of the following are disqualified from enrollment in the sub-study:

- Known hypersensitivity to Gadolinium
- Inability to tolerate or cooperate with MRI (small spaces/claustrophobia)
- Morbid obesity
- Presence of metallic objects or pacemaker

3.3 Recruitment

Recruitment for this sub-study will be limited to subjects who have consented and elected to participate in the ASC01 clinical protocol. Replacement of subjects in this sub-study will occur in the same manner as the parent protocol. Randomized subjects who withdraw from the trial prior to starting rituximab infusion will be replaced. Subjects who discontinue study treatment or withdraw from the trial after initiating the first treatment may not be replaced.

4 Study Design

4.1 Description of Study Design

Twenty subjects from each treatment arm, distributed among all participating sites, will be recruited for this sub-study. Each subject will be studied at baseline (i.e. prior to initiation of study drug) and after 24 weeks, or at time of discontinuation. In addition to the data collection and testing specified in the ASC01 protocol, subjects in RESTORE will undergo comprehensive cardiac MRI evaluation as described in the RESTORE Manual of Procedures (MOP). In brief, this will include short axis, body axial, four-chamber and three-chamber cardiac-gated MRI sequences; pulmonary and aortic angiography in the proximal main pulmonary artery and each of the proximal branch pulmonary arteries; and the ascending aorta; measurement of myocardial perfusion using gadolinium enhanced cardiac MRI in the same views specified above, and measurement of delayed gadolinium enhancement in those views.

4.2 Endpoints

The primary efficacy endpoint will be change in RVEDVI measured by cardiac MRI from baseline to 24 weeks after treatment initiation.

The secondary efficacy endpoints will be as follows:

- Change in RV mass measured by cardiac MRI from baseline to 24 weeks after treatment initiation.
- Change in SV measured by cardiac MRI from baseline to 24 weeks after treatment initiation.

An exploratory endpoint is also defined:

- Cardiac output measured by cardiac MRI

5 Study Objectives

The primary objective of the RESTORE sub-study is to evaluate the therapeutic effect of rituximab on the right ventricle (RV) in patients with SSc-PAH. To achieve this objective, we have developed the following hypotheses:

Primary Hypothesis: Right ventricular end-diastolic volume index, as determined by cardiac MRI, will reduce 24 weeks following rituximab therapy as compared to placebo control, in subjects with SSc-PAH participating in ACE Protocol ASC01.

Secondary Hypotheses:

- Right ventricular mass, as determined by cardiac MRI, will reduce 24 weeks following rituximab therapy as compared to placebo control, in subjects with SSc-PAH participating in ACE Protocol ASC01.
- Stroke volume, as determined by cardiac MRI, will reduce 24 weeks following rituximab therapy as compared to placebo control, in subjects with SSc-PAH participating in ACE Protocol ASC01.

Exploratory Hypotheses:

- Cardiac output, as determined by cardiac MRI, will agree with the main study assessment of cardiac output as well as the standardized Fick-based calculation of cardiac output
- Right ventricular end diastolic volume, as determined by cardiac MRI, will correlate with the standardized Fick-based calculation of pulmonary artery capacitance

6 Treatment of Subjects and Study Measurements**6.1 Subject Clinical Considerations**

Consideration must be given to the need for rate adjustment of intravenous Flolan® during the MRI procedures for those subjects requiring this concomitant background SSc-PAH therapy. Given the requirement for IV extension tubing from the subject to infusion pump while in the MRI scanner, Flolan® flow rate adjustment (increase) will be required to compensate for the longer tubing length to allow for consistent dosing.

Further guidance on this issue may be found in the RESTORE MOP.

